### Regression specifications

In the event that the data distribution suggests a different model would be more suitable, we will run and report these models in addition. Specifically, this will include (but not be limited to) considering hurdle models when evaluating the impact on days on CPPs.

Since we expect the number of censored data points in our time spent on CPP outcome measure to be reasonably small, we use a linear probability model in our main regression specification for research question 3. If the data turns out to be more heavily censored, we will consider employing a tobit model instead. Similarly, we will use a logit model to check the robustness of our regression on unauthorised school absence rates.

### Exploratory Analysis

#### High and low readiness of local authorities

Since the randomisation of the implementation date was stratified by the readiness of local authorities to implement Family Safeguarding, we explore a potential difference in effects of the implementation of Family Safeguarding between high and low readiness authorities.

$$\text{logit}(Y_{iat}) = \beta_0 + \alpha_{0a} + \beta_1 FS_{iat} + \beta_2 HR_a + \beta_3 HR_a * FS_{iat} + \sum_{i=1}^5 \beta_{i+3} I(t=i) + \gamma X_{iat} + \rho Z_{at} + \varepsilon_{iat}$$

Where:

- $HR_a$  is an indicator that is equal to 1 if the authority belongs to the high readiness group that first implements the programme, and 0 if they belong to the 'less ready' group.
- $HR_a * FS_{iat}$  is an interaction term that will allow for differential effects of the model on the local authorities in the high readiness tranche versus the low readiness tranche.  $\beta_3$  will be zero if the intervention affects the likelihood of a child entering care equally in both groups of local authorities.

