## Randomisation

The level of randomisation is at the local authority level. Due to the stepped-wedge evaluation design, we randomise the order in which local authorities implement the programme, in six month intervals, rather than which local authority implements the model. The randomisation will be stratified by the level of readiness of participating local authorities. Each local authority will be classified as either 'high readiness', for those that are in a position to implement the model sooner, and second for the 'low readiness' authorities, for those that will need longer to implement the model. Two local authorities were identified as 'high readiness', and three as 'low readiness'.

The two local authorities classified as 'high readiness' will be randomly assigned to implement the model either first or second. Those classified as 'low readiness' will also have the order randomised in which they will implement the model, following the high readiness local authorities (so they will be the third, fourth, and fifth local authorities to implement the model).

The division of local authorities into more or less ready tranches is meant to avoid implementation failure caused by choosing local authorities to receive the intervention that are not yet ready. The assessment of readiness was conducted by the developing local authority Hertfordshire in collaboration with the Department for Education (DfE). Our strata are thus very small strata (2-3), which normally would be avoided but was necessary in order to be able to implement the evaluation. However it is a notable constraint on our randomisation, that will affect the robustness of our results. This will be reflected in the evidence strength rating awarded to the final study.

To avoid potential contamination, local authorities whose implementation start date has not yet passed have to commit to business-as-usual practices to enable a treatment and control group comparison in each time period. However, they will be given permission to begin preparation to implement, so long as it would not influence the current practice in the local authority.

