For the purposes of this RCT, we will only consider children who have been in touch with children's social care between six-months before the first local authority's implementation date, and six-months after the last local authority's implementation date. We define the implementation date as the date the Family Safeguarding model is considered 'Operationally Live' in the local authority. The Operationally Live date has been set in advance by the Department for Education. When analysing the data, we may change the date we consider the intervention to have gone Operationally Live, if it becomes apparent that there have been significant changes in terms of the timings of the models core activities. This will only be done with the agreement with the Department for Education and consultation with the model developer. Any such changes will be detailed in the report. Specifically, the core activities are as detailed below.

[figure not shown]
By the Operationally Live date:

- Training in Motivational Interviewing and workshops by the model developers should have been delivered to all staff in family safeguarding teams.
- Specialist adult workers should be recruited and in post.

From the Operationally Live date:

- Staff should be using Motivational Interviewing and the parenting assessment and intervention programme with families,
- Staff should be recording case notes using the electronic workbook
- Group case supervision should begin taking place at regular intervals for cases with adult specialist worker involvement.

The diagram below illustrates the randomisation and intended timings of the implementation of Family Safeguarding across the local authorities. The trial period, as indicated in the diagram, takes place from 6 months prior to when the first local authority implements the model (or goes Operationally Live), and continues until 6 months after the final local authority implements the model.

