### ***Sample size and cluster size***

The sample size was derived from the estimated baseline population for our primary outcome, which is the number of children who have been referred in a six month period. We take the average across local authorities that form part of our sample to calculate the average cluster size. The sample size is derived from the average cluster size times the number of local authorities in the trial and the six periods of the stepped-wedge implementation.

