#### **Differential time effects**

We do not consider time effects such as embedding periods in our primary analysis. It may be that Family Safeguarding needs some time to be fully embedded and functional. In that case the treatment will show differential time effects. In this sensitivity analysis, we thus

---

 Wang, R. & De Gruttola, V. (2017): The use of permutation tests for the analysis of parallel and stepped-wedge cluster-randomized trials

include differential treatment effects depending on the time passed since Family Safeguarding has been implemented in the local authority. The regression specification is:

$$\text{logit}(Y_{iat}) = \beta_0 + \alpha_{0a} + \beta_1 FS_{iat} + \sum_{m=0}^M (FS_{iat} \cdot T_{t+m}) \delta_{m+1} + \sum_{i=1}^5 \beta_{i+1} I(t=i) + \gamma X_{iat} + \rho Z_{at} + \varepsilon_{iat}$$

where  $T_{t+m}$  is a binary indicator that equals one if the observation is from a local authority that has been implementing Family Safeguarding for  $m$  periods, and otherwise 0. The coefficients on the interaction effect will shed light on whether authorities experience increasing treatment effects the longer they run Family Safeguarding.

We recognise that the estimation of differential time effects will likely be underpowered due to splitting the treatment effect into separate, time-dependent effects. Nevertheless, we consider this analysis as potentially providing a richer picture of the effects of Family Safeguarding.

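### The readiness interaction coefficient is not zero under equal effects if the effect changes with time since go-live, because readiness group and length of exposure are tied by design

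*Protocol*

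**What the plan says.** Protocol, Exploratory Analysis, High and low readiness of local authorities: the logit model contains a random authority intercept, period dummies, covariates, a single indicator FS for referral after go-live, a readiness indicator HR, and HR×FS. HR "is an indicator that is equal to 1 if the authority belongs to the high readiness group that first implements the programme". The coefficient on HR×FS, β3, "will be zero if the intervention affects the likelihood of a child entering care equally in both groups of local authorities". The section has no term for time since go-live and no caveat about exposure.

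Protocol, Randomisation: two authorities are high readiness and three are low. The high-readiness pair is randomised between first and second place. The low-readiness three are randomised among the remaining places, "so they will be the third, fourth, and fifth local authorities to implement the model". Roll-out is in six-month steps, and the trial period "continues until 6 months after the final local authority implements the model". Sample size and cluster size refers to "the six periods of the stepped-wedge implementation".

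Protocol, Sensitivity Analysis, Differential time effects: "It may be that Family Safeguarding needs some time to be fully embedded and functional". Effects by time since implementation are modelled there, in a separate specification that does not contain readiness.

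**The concern.** The stated reading of β3 needs a condition that the section does not give: the effect must be the same at every time since go-live. If it is not, the average effect seen in an authority depends on how long that authority has been observed under the model, and that is fixed by its readiness group. Randomisation within strata cannot break the link. β3 then mixes any true readiness difference with the difference in exposure, and can depart from zero although the effect profile is identical in both groups.

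At stake is how an exploratory result is read. A reader who follows the sentence would take a non-zero β3 as evidence that readiness changes how well the model works, which bears on which authorities should adopt it.

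**Working it through.** **Inputs from the protocol.** 5 authorities, 6 periods, 1,700 children per cell, baseline 0.06, ICC 0.00722, two-sided 5%, 80% power, MDES 0.0105 (Sample size / MDES calculations; Appendix B).

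**Reproducing the stated MDES.** Hussey-Hughes variance: Iσ²(σ²+Tτ²) / [(IU−W)σ² + (U²+ITU−TW−IV)τ²].
- Total variance is 0.06×0.94 = 0.0564, so τ² = 0.00722×0.0564 = 0.000407 and σ² = 0.0564×0.99278/1,700 = 0.0000329.
- U = 15, W = 55, V = 55. The two brackets are 5×15−55 = 20 and 225+450−330−275 = 70.
- SE = 0.00374, and MDES = (1.96+0.84)×0.00374 = 0.0105, as stated.

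**Exposure by readiness group.** Count full periods since go-live in each treated cell.
- High readiness: 0–4 and 0–3, nine cells, mean (10+6)/9 = 1.78.
- Low readiness: 0–2, 0–1 and 0, six cells, mean (3+1+0)/6 = 0.67.

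**Fitting the planned model with identical profiles in both groups.** The mature effect is set to the MDES, 6.0% to 4.95%: ln(0.0495/0.9505) − ln(0.06/0.94) = −0.203. The embedding curves are assumptions, since the documents give none. The model was fitted to exact expected cell values with fixed authority effects (which absorb HR), period dummies, FS and HR×FS. Rejection is Φ(−1.96−β3/SE) + 1 − Φ(1.96−β3/SE), with SE about 0.098.

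| Curve, same in both groups | β3 | Rejection at nominal 5% |
|---|---|---|
| Constant | 0.000 | 5% |
| Half effect in first period | −0.049 | 8% |
| Linear, 0.2 to 1 | −0.074 | 12% |
| Linear, 0 to 1 | −0.092 | 16% |
| One period late | −0.100 | 17.5% |
| 0, 0.5, then full | −0.117 | 22% |
| Two periods late | −0.134 | 28% |

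Simulation of 2,000 trials per scenario gave 5.1% (constant), 11.7% (linear, 0.2 to 1) and 18.9% (one period late).

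**Adding the outcome window.** The RCT Design Table counts entry to care within 18 months of referral, which is three periods. The Conditions section accepts that control children may meet the model later. Each child's effect was therefore averaged over the 18 months from referral, with no effect before go-live. The weights for when care entry occurs are assumed: flat, or exponential decay with a constant of 6 or 2 months.

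| Embedding | Flat | 6 months | 2 months |
|---|---|---|---|
| None (immediate) | +0.10 (16%) | +0.07 (11%) | +0.04 (7%) |
| One period late | +0.05 (7%) | −0.01 (5%) | −0.07 (10%) |
| Linear over one year | +0.04 (7%) | −0.01 (5%) | −0.06 (9%) |
| Two periods late | −0.04 (7%) | −0.09 (15%) | −0.12 (24%) |
| Linear over five periods | −0.04 (7%) | −0.06 (9%) | −0.07 (11%) |

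The positive values arise because the high-readiness authorities have only one and two control periods, all close to go-live. Their control children are the most exposed to later contact, so their contrast is diluted most. The low-readiness authorities have three, four and five control periods.

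**Changed model.** FS is replaced by five exposure-period indicators common to both groups, and HR×FS is kept. The design matrix has full rank (16 of 16), because both groups have exposure periods 0–2. Under every scenario in both tables, expected β3 returns to about 0 and rejection to 5% (4.4% to 5.3% in simulation). The SE of β3 rises from about 0.10 to 0.13.

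**The case against.** The analysis is labelled exploratory, attaches no decision to β3, and leaves the primary analysis untouched. The 5% level is stated under the primary analysis, where small-cluster inference is still open, so the rejection rates above assume a Wald test that the readiness section does not prescribe. The sentence is a usual gloss on an interaction coefficient and is true inside its own model. Differential time effects would be reported in a separate sensitivity analysis, and the Randomisation section already concedes that the readiness constraint weakens the results.

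Much of this stands, and it makes the point a modest one. It does not remove it. The protocol fixes both the formula and the interpretation, so this is not detail left to an analysis plan. Neither the separate time-effects model nor the general concession is linked to β3.

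A reader might go further and infer that the test will find a difference, and that it will favour the ready authorities. The documents do not support that. At an effect the size of the MDES, most trials would show no significant β3 under any curve tried. Once the outcome window and later contact are allowed for, the sign can go either way, and an effect that fades would also reverse it. Much higher rejection rates need an effect well above the MDES, which the protocol does not state.

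**Conclusion.** The point holds in a limited form. The stated interpretation of β3 is correct only for an effect that is constant over time since go-live, a condition that the section omits and that the protocol elsewhere doubts. With identical profiles in both groups and a mature effect at the MDES, β3 is biased by about −0.05 to −0.13, roughly a quarter to two-thirds of the full effect (0.049/0.203 = 24%; 0.134/0.203 = 66%), with 8% to 28% rejection. With the outcome window included, the range is about +0.10 to −0.12 with 5% to 24% rejection.

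That bias arises whenever the effect varies with exposure follows from the design. Its size and sign rest on assumed embedding curves and timing weights. No direction is established.

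**What to change.** In the readiness model, replace the single FS term with indicators of time since go-live (exposure periods 0 to 4) common to both groups, and keep HR×FS. The Differential time effects section already defines such indicators. Reword the sentence to say that β3 is zero if the log-odds effect at the same time since implementation is equal in both groups.

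Report the five authority-specific effects with intervals beside β3, and state that the comparison of two authorities with three is descriptive. This is needed because the changed model does not remove ordinary variation in effect between authorities, which can still look like a readiness difference.

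The cost is one formula and a few lines of text, with no new data. The price is precision: the SE of β3 goes from about 0.10 to 0.13.

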## **Cost Benefit Analysis**

Our main analysis focuses on potential effects of Family Safeguarding on children’s social care outcomes. Given the opportunity for the model to not only improve outcomes but also realise significant cost savings for local authorities, we will investigate the implicit cost savings our estimates suggest.

The main focus of this analysis will be on any savings or costs realised through a change in the number of children that become looked after. This will be informed by the coefficient of our primary analysis and average cost estimates per looked after child. Note that this will focus on the savings or costs realised by the (average) number of cases where children that were involved with statutory services did or did not go on to become looked after due to Family Safeguarding. We will also gauge cost savings in other areas of children’s social care measured in our main analysis if applicable.

## **Data handling**

### **Data gathering**

Data will be collected directly from local authorities. We limit ourselves to asking for administrative data that has to be recorded for statutory returns so that our analysis will not need further data collection.

Data	Collection Point	Source
Individual-level administrative data on the sample populations (including treatment condition, and individual covariates)	In twelve month intervals, starting after the first 12 months of the trial period until the end of the trial period (six months after the last implementation date)	Directly from local authorities
Individual-level administrative data on outcome measures	In 18 month intervals, starting at the end of the trial period until 36 months after the trial period (42 months after the last implementation date)	Directly from local authorities

Local-authority level administrative data (summary statistics of the previous six months) 	In six month intervals, starting at the end of the baseline period (the date the first local authority goes Operationally Live) until the end of the trial period (six months after the last implementation date)	Directly from local authorities
---	---	---------------------------------

### **Data protection**

The underlying data used to conduct this analysis consists of administrative data from local authorities funded by the Department for Education to introduce Family Safeguarding as part of the Strengthening Families, Protecting Children programme, with the exception of the Trailblazer. The data about individuals requested from each local authority will be pseudonymised. We will not request any ‘instant identifiers’ (that would allow us to point to an individual in the dataset) or ‘meaningful identifiers’ (which would allow identifying someone through linking the data to another dataset, beyond the local authorities administrative datasets). We will require ‘meaningless identifiers’ (data variables used within the local authorities dataset or datasets, but have no meaning beyond these datasets’ boundaries) to track individuals over time.

This section is structured according to the guidance given by the Information Commissioner's Office, which “covers the General Data Protection Regulation (GDPR) as it applies in the UK, tailored by the Data Protection Act 2018”.

### **Principles of the GDPR**

#### Principle (a): Lawfulness, fairness and transparency

##### 1. Lawfulness:

WWCSC will be a data controller in common with each local authority for each of their respective datasets. WWCSC decided to process the data and decided the purpose of its processing, what data should be collected and which individuals to collect data about. The data is collected by the local authorities for their own purposes. They determined that they would share the data with WWCSC for processing. The legal basis for WWCSC processing the data is legitimate interest.

Legitimate interest is a three part test:

##### 1) Purpose test: are you pursuing a legitimate interest?

---

 If the data is not available in monthly intervals, we will try and get as frequent intervals as possible. As a last resort, we will use yearly data that is publicly available online.

 Information Commissioner's Office, Guide to the General Data Protection Regulation (GDPR). <https://ico.org.uk/for-organisations/guide-to-data-protection/guide-to-the-general-data-protection-regulation-gdpr/>

We are a charity, whose purpose is to improve the evidence base in children's social care. We consider the processing of the data to be in our legitimate interests because it will enable us to produce research in this area, which will benefit local authorities, in particular senior leaders who make decisions about practice models, as well as the Department for Education in future funding decisions.

2) Necessity test: is the processing necessary for that purpose?

The processing is necessary for the purpose because processing individual-level data allows us to conduct analysis which is better powered to detect the impact of Family Safeguarding, and which allows us to better control for the circumstances of the individual which may affect the outcome. Both of these factors mean that we are more likely to be able to provide meaningful research which can be used to inform practice, with downstream effects for children involved in statutory social care.

3) Balancing test: do the individual's interests override the legitimate interest

We will publish a privacy notice on our website to give general notice of this processing, prior to it taking place. While the data is quite sensitive and on a population which includes vulnerable children, the data will be pseudonymised, with us being very unlikely to be able to identify any child or family. The data will be stored securely. We believe this processing falls within generally socially acceptable uses of this kind of data - it is scientific research in the public interest by a charity and for the benefit of a vulnerable group. Alongside the privacy notice, we will include a form which individuals can fill in to uphold their individual data rights.

We therefore believe that the individuals' interests do not override our legitimate interest in this processing.

The legal basis for processing special category data is that it is necessary for archiving, scientific, historical research or statistical purposes (point (e) of section 10 of the DPA which refers to (j) (archiving, research and statistics) of Article 9(2) of the GDPR). The project meets condition (4) in Part 1 of Schedule 1:

(a) is necessary for archiving purposes, scientific or historical research purposes or statistical purposes,

This processing constitutes scientific research as it will be used to create evidence on pre-defined, specific hypotheses around what works to improve outcomes for children who have undergone statutory intervention, in order to increase the knowledge base in this area. The special category data we are using is data concerning ethnic group and health, specifically disability status. Not being able to assign ethnic group or disability status to our data would limit the scientific value of this research because they are likely moderators of social care outcomes. The likelihood of children to enter care also varies significantly by ethnic group and is thus important to control for when trying to gauge the impact of Family Safeguarding on children's services.

(b) is carried out in accordance with Article 89(1) of the GDPR (as supplemented by section 19)

### Organisational and Technical Arrangements

“Those safeguards shall ensure that technical and organisational measures are in place in particular in order to ensure respect for the principle of data minimisation. Those measures may include pseudonymisation provided that those purposes can be fulfilled in that manner.”

The data will be pseudonymised i.e. it can no longer be attributed to a specific data subject without the use of additional information. We are not requesting any ‘instant identifiers’ (e.g. name or address) or ‘meaningful identifiers’ (identifiers that allow linking to other datasets, beyond the local authorities’).

